8.1.7. Secondary Safety Endpoints

- (1) Rate of conversion to thoracotomy or secondary intervention. Whether subjects require

conversion to open thoracic surgery or secondary interventional procedures due to new-onset aortic dissection caused by the index procedure.

- (2) Rate of major adverse events occurring within 30 days after surgery. Refers to all-cause mortality, myocardial infarction, ischemic stroke or respiratory failure occurring within 30 days after surgery. More specifically, myocardial infarction refers to a drastic reduction or complete interruption of the coronary blood supply due to coronary artery disease, resulting in severe and prolonged acute ischemia of the corresponding myocardium, leading to necrosis of cardiomyocytes. Ischemic stroke refers to the end result of necrosis of brain tissue caused by narrowing or occlusion of the arteries supplying blood to the brain or insufficient blood supply to the brain. Respiratory failure is defined as a state resulting in significantly prolonged intubation, tracheotomy, deterioration of lung function, or other fatal outcomes.
- (3) Rate of aortic aneurysm-related mortality at 12 months post operation. Refers to mortality caused by a ruptured aortic aneurysm or endovascular interventional treatment.
- (4) Incidence of severe adverse events. Refers to an event that occurs during the clinical trial that results in mortality or serious deterioration in patient health, including a fatal illness or injury, a permanent defect in body structure or body function, or an event that requires medical or surgical intervention to avoid one or more permanent defects in body structure or body function.
- (5) Incidence of device-related adverse events. Device-related adverse events refer to an adverse medical event related to the use of a device that occurs during the course of the clinical trial. However, a distinction should be made with respect to normal postoperative stress response, such as fever and chest and back discomfort, which, in the judgment of the investigator, need not be recorded as an adverse event. Recording device-related adverse events will be applicable for conditions that are deemed by the investigator to be definitely related, possibly related, or of indeterminate relationship, to the test device.

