14.1.2. Causality Assessment between Adverse Event and Investigational Medical Device

1.Relatedness to the investigational product:

Related to the investigational medical device: (1) There is a reasonable temporal relationship. (2) The event is a known risk of the device or can be explained by its mechanism of action. (3) The injury improves or resolves after cessation of device use. (4) The injury recurs upon rechallenge with the device. (5) The event cannot be explained by other confounding factors. If all five criteria are met, the relationship is assessed as "Definite"; if at least two criteria are met, it is assessed as "Possible".

Not related to the investigational medical device: (1) There is no reasonable temporal relationship. (2) The event type cannot be caused by the investigational medical device. (3) The event can be explained by concomitant devices/medications, disease progression, or other therapeutic interventions. (4) Definitely Not Related: All 3 criteria are satisfied. (5) Probably Not Related: At least 1 criterion is satisfied.

2. Relatedness to the procedure:

Definitely related: The reaction is consistent with the known reaction profile of the procedure.

Probably related: The reaction is consistent with the known reaction profile of the procedure; the patient's clinical condition or other treatments may also contribute to the reaction.

Probably unrelated: The reaction is poorly consistent with the known reaction profile of the procedure; the patient's clinical condition or other treatments may account for the reaction.

Definitely unrelated: The reaction is inconsistent with the known reaction profile of the procedure; the patient's clinical condition or other treatments can fully explain the reaction; the reaction resolves upon improvement of the underlying disease or discontinuation of other treatments,

and reappears following reintroduction of such other treatments.

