14.2. Severe Adverse Events

A Serious Adverse Event refers to any untoward medical occurrence during a clinical trial of a medical device that results in death or severe deterioration of health status, including fatal disease or injury, permanent impairment of body structure or function, requirement for hospitalization or prolongation of hospitalization, medical intervention required to prevent permanent impairment of body structure or function, fetal distress, fetal death, congenital anomaly or congenital defect.

Planned hospitalization due to a pre-existing disease or surgery specified in the clinical trial protocol that does not cause severe deterioration of health status shall not be regarded as a Serious Adverse Event.

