14.4. Reporting Procedures

14.4.1. Adverse Events

Adverse event data will be collected throughout the study, and the investigators will record and monitor all adverse events in the appropriate eCRF until recovery or stabilization occurs.

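### The SAE and device-related AE endpoints rest on definitions that conflict within the protocol, so their incidences depend on the section applied and can be understated

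*Protocol*

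**What the plan says.** **Serious adverse events.** The endpoint in 8.1.7(4), repeated in the Trial Protocol Summary, covers death or a serious worsening of health, names fatal conditions and lasting defects as instances, and closes its list with "an event that requires medical or surgical intervention to avoid one or more permanent defects in body structure or body function". Section 14.2, the dedicated definition, also lists "requirement for hospitalization or prolongation of hospitalization", as well as fetal and congenital outcomes. It exempts planned admissions that involve no severe deterioration.

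**Device-related adverse events.** The endpoint in 8.1.7(5) counts events the investigator judges to be "definitely related, possibly related, or of indeterminate relationship, to the test device". Section 14.1.2 provides four levels: Definite (all five related criteria), Possible (at least two of the five), Definitely Not Related (all three unrelated criteria), and a fourth defined as "Probably Not Related: At least 1 criterion is satisfied". One of the five related criteria is "The injury recurs upon rechallenge with the device".

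**Recording.** Section 8.1.7(5) sets apart normal postoperative stress responses, "such as fever and chest and back discomfort, which, in the judgment of the investigator, need not be recorded as an adverse event". Section 14.4.1 has investigators "record and monitor all adverse events in the appropriate eCRF until recovery or stabilization occurs". The notes to the procedure chart in 8.2.1 call for all adverse events from Visit 2 onward, and the secondary endpoint text of 9.4.2 calls for all of them to be recorded in detail.

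**Analysis.** Section 9.4.2 gives secondary safety endpoints frequencies and percentages only, with no test.

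**The concern.** These are two of the five secondary safety endpoints, and 8.1.2 names both among the main safety endpoints of a pre-market, single-arm trial. No control arm shares the same definitions, so a definitional shift passes straight into the reported rate.

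The conflicts lie in rules the protocol does state, not in detail it leaves to an analysis plan. They also govern what the eCRF captures. A tabulation choice can be revisited after database lock, but an event that was never entered cannot be recovered.

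The relatedness overlap matters because one of the two available classes is counted and the other is not. The investigator makes that choice knowing the treatment. The independent laboratory in 8.1.9 is for imaging data, and the protocol gives it no role in judging causality.

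**Working it through.** The protocol states no expected rate for either endpoint, so there is no figure to reproduce.

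**1. SAE definitions side by side**

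| Criterion | 8.1.7(4) and synopsis | 14.2 |
|---|---|---|
| Death or serious deterioration in health | listed | listed |
| Fatal illness or injury | listed | listed |
| Permanent defect | listed | listed |
| Intervention to prevent a permanent defect | listed (medical or surgical) | listed (medical) |
| Hospitalisation or longer stay | not listed | listed |
| Fetal or congenital outcome | not listed | listed |

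If medical intervention in 14.2 is taken to include surgery, the 14.2 list contains the 8.1.7(4) list. A literal reading of 8.1.7(4) then gives an equal or lower incidence. Fetal and congenital items should matter little, because pregnant patients are excluded at entry. Hospitalisation is the material difference.

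Let I be the proportion of subjects with an SAE under 14.2, and h the share of those who qualify by hospitalisation only. The literal 8.1.7(4) incidence is I × (1 − h). Both inputs are assumptions:

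- I = 20%: h = 0 gives 20%; h = 30% gives 20% × 0.70 = 14%.
- I = 40%: h = 0 gives 40%; h = 30% gives 40% × 0.70 = 28%.

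The result spans 14% to 40%. For a given I the loss is I × h, from 0 up to 40% × 0.30 = 12 percentage points.

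**2. Relatedness classes in 14.1.2**

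Call the related criteria R1 to R5 (timing; known risk or mechanism; improvement on stopping; recurrence on re-exposure; no other explanation) and the unrelated criteria N1 to N3 (no timing; device cannot cause it; other explanation). Assume N1 negates R1, N3 negates R5, and N2 cannot hold together with R2. R1, R3, R4 and R5 are free (2⁴ = 16 combinations), and R2 with N2 has 3 consistent states, so there are 16 × 3 = 48 patterns:

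| Related side | Unrelated side | Patterns |
|---|---|---|
| Possible | Probably Not Related | 28 |
| Possible | Definitely Not Related | 1 |
| Possible | none | 7 |
| Definite | none | 1 |
| none | Probably Not Related | 8 |
| none | Definitely Not Related | 3 |

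If R3 and R4 are assumed unobservable for a permanent implant, 4 × 3 = 12 patterns remain. Five are Possible, and 3 of those 5 are also Probably Not Related. The other 7 fall only on the unrelated side. These are counts of rule patterns, not event frequencies.

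A concrete case: timing is plausible (R1), the event is a known device risk (R2), and disease progression could also explain it (N3). Two related criteria make it Possible and one unrelated criterion makes it Probably Not Related. No text says which prevails.

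None of the 48 patterns is left unclassified, so 14.1.2 gives no content, even by default, to the indeterminate class that 8.1.7(5) counts.

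**3. Recording rules**

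Section 8.1.7(5) lets the investigator leave fever and chest or back discomfort unrecorded. Sections 8.2.1, 9.4.2 and 14.4.1 require all adverse events to be recorded, and none repeats the exemption. Applying it can only lower the count.

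**The case against.** A reader might infer that both incidences will be understated. The documents do not support that.

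- **SAEs.** Both definitions open with death or serious deterioration and continue with a list introduced as inclusive. In 14.2 hospitalisation is itself an item in that list, so 8.1.7(4) may be read as non-exhaustive and many admissions would qualify as serious deterioration. Nothing says SAEs collected under 14.2 are re-filtered under 8.1.7(4). If they are tabulated under 14.2, nothing is lost. This stands against certainty. It does not remove the conflict, because no passage says which definition governs the endpoint.
- **Relatedness.** The overlap has no fixed direction, since a doubly classified event is counted or not according to how it is coded. Counting indeterminate events works against understatement.
- **Events with no class.** One might infer that an event meeting a single related criterion and no unrelated one falls through. If N1 and N3 both fail, R1 and R5 both hold under the assumptions above, so the event is Possible. A gap arises only if the confounders in R5 are read more widely than the explanations in N3.
- **An unattainable Definite class.** Improvement on stopping and recurrence on re-exposure can hardly be shown for a permanent implant. That distorts grading but not the incidence, because 8.1.7(5) pools Possible with Definite.
- **Recording.** Normal recovery could be regarded as not an adverse medical event at all, and the inclusion of fever in 14.4.3 is a list of potential events, not a recording rule. That reconciliation is reasonable, but the protocol does not state it, and the line is left to individual judgment with no record to check.
- **Impact.** Strokes are poor examples of what might be lost. Major stroke within 12 months is in the primary endpoint and ischemic stroke within 30 days is in the major adverse event endpoint, both regardless of relatedness.

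**Conclusion.** The point holds as a set of three internal conflicts. The SAE incidence under a literal 8.1.7(4) is equal to or below that under 14.2. The device-related incidence depends on an overlap that no rule resolves and on a counted class that is not defined. Some events may go unrecorded under one section although others require them. The supported conclusion is that the incidences can be understated, not that they will be: the SAE and recording conflicts can act only downward, while the relatedness overlap can act either way.

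The documents give no basis for a size. The 14% to 40% span rests entirely on assumed inputs and includes no effect. Because both endpoints are described without a test or success criterion, the primary endpoint and the sample size are unaffected. The conflicts are still worth correcting, since these are headline safety rates in a single-arm pre-market trial and the correction is cheap.

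**What to change.** - **SAE definition.** Use the single 14.2 definition in the synopsis and in 8.1.7(4), making clear that intervention there includes surgery.
- **Relatedness.** Make the 14.1.2 device-relatedness classes mutually exclusive and state which prevails when criteria from both sides are met. Align the classes with those counted in 8.1.7(5), and define indeterminate. Which precedence rule to adopt is for the sponsor and investigators; the documents show only that one is needed.
- **Recording.** Record all adverse events and flag expected postoperative reactions in the eCRF instead of omitting them, so that rates can be shown with and without them.

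The cost is protocol wording, eCRF edits, slightly more data entry and possibly somewhat higher reported incidences. The sample size and the primary analysis do not change.

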- Concomitant medication records: medications relevant to the evaluation of the investigational device (including anticoagulants, antiplatelet agents, antihypertensives, lipid-lowering drugs, hypoglycemic drugs, antibiotics, etc.); and medications administered for underlying diseases, concomitant diseases, or adverse events.
- Adverse event records: all adverse events starting from Visit V2.
- In the event of a stroke in a subject, the modified Rankin Scale (mRS) score shall be collected at 90 days after the stroke onset.
- If feasible, laboratory data obtained within 15 days prior to subject enrollment (before signing the informed consent form), as well as aortic CTA, cerebral CTA or Magnetic Resonance Angiography (MRA), echocardiography, and 12-lead ECG data obtained within 30 days prior to signing the informed consent form, may be used for baseline assessment without repeat testing.
- Long-term follow-up CTA data shall be collected at postoperative Years 2, 3, 4 and 5 (± 30 days), with records of adverse events and concomitant medications related to adverse events.*Relevant examinations and data collection shall be performed only in patients randomized to the test group.

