4) Secondary Endpoints

Technical success immediately post-procedure, aortic aneurysm progression control rate, incidence of Type I or Type III endoleak, incidence of aortic stent graft migration, postoperative patency rate of branch vessels, incidence of conversion to open thoracic surgery or secondary interventional procedure, major adverse event rate within 30 days post-operation, aortic aneurysm-related mortality at 12 months post-operation, incidence of serious adverse events, and incidence of device-related adverse events.

Statistical description shall be performed for secondary efficacy indicators, with frequencies and percentages calculated. FAS (Full Analysis Set) and PPS (Per Protocol Set) analyses shall also be conducted.

Statistical description shall be performed for secondary safety indicators, with frequencies and percentages calculated. The SS (Safety Set) analysis shall be adopted as the primary approach.

The Kaplan-Meier method shall be used to estimate the survival rate and its 95% confidence interval, with Kaplan-Meier curves plotted accordingly.

Descriptive statistical analysis shall be performed for the changes of all laboratory parameters before and after the trial. All adverse events occurring during the trial shall be recorded in detail; descriptive statistical analysis of adverse events shall be conducted with a list attached.

In addition to the above statistical methods, detailed and additional exploratory analyses may be required, which shall be confirmed in the Study Report and Statistical Analysis Plan (SAP)..

9.5. Statistical methods for all data, including the handling of missing, unused or erroneous data (including premature discontinuation and withdrawal) and inconsistent data.

A Statistical Analysis Plan (SAP) shall be developed prior to study initiation. After database lock, statistical analysis shall be performed in accordance with the SAP, and a statistical analysis report shall be generated based on the results.

(1) Handling of missing data: Missing data shall be handled according to the analysis set in which they are included. Missing data for the primary endpoint in the Full Analysis Set (FAS) shall be classified by reason as follows:

Missing data clearly due to unsatisfactory efficacy: loss to follow-up or missing primary efficacy data resulting from adverse events, death, etc., related (or possibly related) to the investigational device or aortic dissection.

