14.1. Adverse Events

An adverse medical event that occurs during the conduct of a clinical trial of a medical device, regardless of whether it is related to the investigational medical device.

Any pre-existing disease documented in medical history during the screening period shall not be considered an adverse event unless there is a change in its nature, severity, frequency, or required intervention.

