14.4.3. Potential Adverse Events

Allergies, aortic dissection enlargement, aortic dissection rupture, arterial thrombosis, arterial injury, arterial perforation, arteriovenous fistula, pseudoaneurysm, hemorrhage/hematoma, bowel syndrome, pulmonary syndrome, heart failure/myocardial infarction, intermediate surgery, death, edema, sexual dysfunction, fever, renal insufficiency/failure, wound syndrome, air embolism and device complications, including: incorrect release position, stent migration, stent breakage, endoleak and coating rupture.

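### The device-related adverse event endpoint lets investigators leave supposed normal postoperative reactions unrecorded, without an objective criterion and against the protocol's own duty to record all adverse events

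*Protocol*

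**What the plan says.** Incidence of device-related adverse events is the fifth secondary safety endpoint (section 8.1.7(5); same wording in the synopsis). The definition asks that a normal stress reaction to the operation be kept apart, "such as fever and chest and back discomfort, which, in the judgment of the investigator, need not be recorded as an adverse event". The sentence after it says that events the investigator considers definitely related, possibly related or of indeterminate relationship to the device are to be recorded.

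Elsewhere the protocol states the recording duty without exception:
- Section 8.2.1, notes to the schedule: "Adverse event records: all adverse events starting from Visit V2". Visit 2 is the day of surgery.
- Section 9.4.2, item 4: "All adverse events occurring during the trial shall be recorded in detail".
- Section 14.4.1: "the investigators will record and monitor all adverse events in the appropriate eCRF until recovery or stabilization occurs".
- Section 21.4(8) puts the same duty on investigators, and section 8.4(6) has monitors confirm that it was met.

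Section 14.1 counts an untoward event "regardless of whether it is related to the investigational medical device". Section 14.4.3 includes fever among the potential adverse events: "edema, sexual dysfunction, fever, renal insufficiency/failure, wound syndrome".

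**The concern.** The permission acts when data are captured, not when they are analysed. An event that is never entered has no severity, relatedness or outcome, and no later analysis can restore these. The person deciding is the investigator, who under section 8.2 also performs the operation. Section 8.1.2 describes a single-arm study, and the protocol describes no blinding. A monitor who finds a fever in the source notes and no matching entry cannot tell an omission from a permitted exclusion.

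At stake is a named secondary safety endpoint of a pre-market study whose 12-month results go to the regulator (sections 4.2 and 8.1.4.6). Its reported value would depend partly on recording habits at each site.

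**Working it through.** The protocol gives no expected rate of fever, of chest or back discomfort, or of device-related adverse events. There is no figure to reproduce, so the check is mainly a comparison of sections.

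**1. Definition.** Section 14.1 counts events whatever their relation to the device. Its one stated exclusion is "Any pre-existing disease documented in medical history during the screening period shall not be considered an adverse event", and even that falls away if the condition changes in nature, severity, frequency or need for intervention. A postoperative stress reaction is not excluded.

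**2. Recording duty.** Sections 8.2.1, 9.4.2, 14.4.1 and 21.4(8) all say that every adverse event is recorded. Section 8.2.1 starts the clock on the day of surgery, so the early postoperative period is covered. None of them, nor the monitoring duty in section 8.4(6), refers to the exception in section 8.1.7(5).

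**3. Listed events.** Fever is in the list in section 14.4.3. Chest or back discomfort is not. The conflict with that list therefore holds for fever alone.

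**4. The endpoint's own inclusion rule.** Under section 14.1.2 an event is possibly related if at least two of five criteria are met. A reasonable time relationship is one. A known risk of the device, or an explanation by its mechanism, is another. Fever soon after implantation meets the first. It may meet the second if the list in section 14.4.3 is read as known risks. That reading is arguable, because the list names device complications as a separate group and fever is not in it. Where both are met, the last sentence of section 8.1.7(5) requires recording of an event that the sentence before it allows the investigator to skip.

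**5. Other capture.** The schedule in section 8.2.1 has body temperature, within the physical examination, at Visits 1, 2 and 3 only. Concomitant medication, including antibiotics, is recorded. The scheduled symptom assessment is the modified Rankin Scale, which does not ask about chest or back discomfort. Some traces of fever may survive, but not as an adverse event with severity, causality and outcome.

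**6. Direction and unit of size.** Let N be the number of subjects and x the number with at least one device-related adverse event under full recording. Let k be the number of those whose only such event is left out.
- Rate under full recording: x/N.
- Reported rate: (x − k)/N.
- Difference: −k/N, which is never positive.
- With the 90 planned subjects and k = 1: 1/90 = 1.1 percentage points.
- With the 72 targeted valid cases (section 8.1.4.8) and k = 1: 1/72 = 1.4 percentage points.

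The protocol contains nothing from which k could be estimated.

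**The case against.** The strongest defence is that a normal response to an operation is not an adverse medical event at all, so a duty to record all adverse events is not breached by leaving it out. Listing fever as a potential adverse event does not make every fever one. The clause is also permissive and limited to reactions judged normal. Fever from infection, or chest pain from a dissection, would not qualify and would stay recordable.

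The limits on scope stand. The defence of the wording does not, because the protocol gives no objective criterion, such as severity or duration, for telling a normal reaction from an adverse one, and section 14.1 makes no such exclusion. The line is drawn by unrecorded judgement, so nobody can check afterwards where it was drawn.

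A reader might infer more, and the protocol does not support it:
- **That all fever and all chest or back discomfort is removed from the safety data.** The clause covers only reactions judged normal, and temperature is still measured at Visits 2 and 3.
- **That serious aortic complications could go uncounted.** Serious events remain reportable whatever their relation to the device (sections 14.2 and 14.4.2), and aortic CTA is scheduled during follow-up.
- **That a large, stated share of subjects is affected.** No frequency is given, and any percentage would be a guess.
- **That the rates cannot be compared with those of other devices.** That depends on how other studies recorded events, which the protocol does not show.

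**Conclusion.** The point holds as an internal contradiction with a one-sided effect. The permission in section 8.1.7(5) and the synopsis cannot be squared with sections 8.2.1, 9.4.2, 14.1, 14.4.1 and 21.4(8), nor, for fever, with section 14.4.3. Compared with full recording, it can only lower the incidence of device-related adverse events, and it may do so unevenly across sites.

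The size is unknown. The unit is 1.1 percentage points per affected subject out of 90. This assumes that the omitted event would have counted as device-related under section 14.1.2 and was that subject's only such event. Events judged related to the procedure but not to the device would not move this endpoint.

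The consequence is bounded. Secondary safety endpoints are analysed descriptively (section 9.4.2). The primary endpoint of death or major stroke, its comparison with the performance criterion, and serious adverse event reporting are untouched. The point should be corrected, but it does not threaten the main conclusion of the trial.

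**What to change.** Reconcile the sections as follows:
- In section 8.1.7(5) and in the synopsis, delete the permission to leave these reactions unrecorded.
- Record them as adverse events with severity, relatedness and outcome, and add one eCRF field that flags an expected postoperative response.
- Report the incidence of device-related adverse events with flagged events included and, as a supporting line, without them.

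This keeps the sponsor's distinction but moves it from data capture to analysis, where it can be audited, and brings the endpoint into line with the recording duties. Stating objective criteria for the exclusion and amending every conflicting section would also remove the contradiction, but the excluded events would still go unrecorded.

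The cost is one sentence in two places, one eCRF field, somewhat more adverse event entry and a less favourable reported rate. Under section 15.3, a change to the protocol or case report form during the trial also needs ethics committee approval.
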